6.2.2 FORMULATION, APPEARANCE, PACKAGING, AND LABELING

Formulation and Appearance

The details of formulation are given in [Section 6.1.1](#). The IP is a colorless gel at room temperature.

Packaging

The IP will be packaged in to lacquered aluminium tubes in the quantity of 15 g per tube. The tubes will be placed in cartons which has product information and kit number printed on it (Table 4). Each carton will contain one tube. Each kit will contain 4 such cartons and two boxes of sterile gel measurement strips. Sufficient number of such kits will be made available to ensure sufficient supply of IP for the Study.

Table 4 Labelling information of Galnobax®

Galnobax® Topical Gel Study code: NG-A16		
Kit No.:		
Topical gel contains		Net Wt.
Vehicle or Esmolol Hydrochloride	14% w/w	15 g
Preservative: Benzalkonium chloride solution (50%) 0.26% w/w		
Batch No.:		Mfg. Lic. No.:
Sponsor: NovaLead Pharma Private Limited, Pune, INDIA		
Manufacturer:		
Store in cool environment		
Mfg. Date:		Exp. Date:
FOR CLINICAL TRIAL USE ONLY. NOT TO BE SOLD.		
FOR EXTERNAL USE ONLY		
Caution:		
Keep out of reach of children. In case of Emergency, contact your study doctor or Local Emergency Services		
Subject No.: To be written by study site		
Investigator's name: To be written by study site		
Investigator Contact Number: To be written by study site		
Name of the Institution: To be written by study site		
Visit No.: To be written by study site		
Date of dispensing: To be written by study site		
<hr/>		
Kit No.:		
Subject No.: To be written by study site		
Visit No.: To be written by study site		
Date of dispensing: To be written by study site		

The manufacturer will label the tubes, cartons and kits. In case additional IP is required for any Subject, new kit with same treatment will be issued.

6.2.3 PRODUCT STORAGE AND STABILITY

IP will be stored at 15 to 25°C at the warehouse and at the investigational sites. Upon dispensing to the Study Nurse, instruction will be given to store in refrigerator as far as possible and if not available, in dry and cool environment.

6.2.4 PREPARATION

The IP will be manufactured under Good Manufacturing Practice (GMP) conditions and following all regulations of CDSCO as well as State FDA.

6.3 MEASURES TO MINIMIZE BIAS: RANDOMIZATION AND BLINDING

This is a double-blind study wherein the Investigator, the Sponsor, the Subject, the CRO and the Study Nurse Coordinator will be kept blinded to the randomization throughout the Study. There will be one unblinded Investigator per site who will administer the treatment during each treatment visit of the Subject as well as dispense the IP to the Study Nurse and the SoC material to the Subject. The Study Nurse who will administer treatment to the Subject (twice daily during Treatment Phase) will be unblinded. However, the unblinded Investigator and Study Nurse will still remain blinded to whether the Study drug applied is Galnobax® or Vehicle gel. The blinding of the Subject will be ensured by the Study Nurse by using shield while treating the Target Ulcer.

In case the Subject is staying far from the site (i.e. 40 km or more from the site) and/or Nurse is unable to visit every week to the site for treatment compliance check, following procedure will be followed for IP transport and compliance check: IP will be issued to the study Nurse at the time of the randomization visit along with study diary in an aluminum box having a lock. One key of this lock will be with the study Nurse and other with the unblinded CRC at the site. At the time of weekly site visit of the Subject, study Nurse will keep used IP tubes and Study diary in this box which will be locked and sent to the site with the Subject. Site unblinded CRC will take aluminum box from the subject and will check IP compliance as well as study diary. The IP will be reissued to the nurse after weighing the tubes and new study diary will also be issued (through which new dose of the subject will be conveyed to the Nurse). These materials will be kept in the aluminum box which will be locked and given to the Subject for handing over it to the study Nurse. This process will continue during all treatment visits.

While the IP compliance will be verified by the unblinded Investigator, the Target Ulcer Closure will be decided and confirmed by the blinded Investigator, thus mitigating any bias.

Unblinding will be done only if necessary for the welfare of the Subject or in the case of emergency suspected to be IP related. If such emergency is clearly not IP-related in the opinion of the Investigator, the Subject management can be done without the need of unblinding. Standard norms and procedures for unblinding will be followed.

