4 STUDY DESIGN

4.1 OVERALL DESIGN

This Study is a Phase 3, multicenter, randomized, double-blind, parallel-group Study designed to evaluate the safety and efficacy of Galnobax® plus SoC versus only SoC, in treating DFU in adults with diabetes mellitus (DM). In addition, Study is designed to evaluate safety of Vehicle plus SoC versus only SoC in Subjects with DFU to investigate deleterious effects of Vehicle on wound healing, if any.

For this purpose, the Subjects will be randomized in 3:3:1 ratio into one of the following groups:

- Group 1: Galnobax® 14% gel plus SoC
- Group 2: SoC only
- Group 3: Vehicle plus SoC

Total number of Subjects in the Study: This Study will have FAS Population (Efficacy Evaluable Population) of a minimum of 240 Subjects in Group 1 and Group 2 (minimum of 120 in each Group). To ensure this and assuming 20% drop out rate, the population of two groups would be maximum of 300 Subjects. In addition, for investigating the effect of vehicle on wound healing, Vehicle plus SoC group will recruit up to 50 Subjects. Thus, overall 350 Subjects will be recruited in the Study.

No. of investigational sites: This Study will be conducted at approximately 40 sites across India with competitive recruitment amongst sites.

Maximum duration of a Subject in the Study: The maximum total duration of Subject in the Study will be 25 weeks spread over three phases in following sequence:

- Screening Phase of 1-week (7 + 3 days)
- Treatment Phase of a maximum of 12-weeks (84±3 days) starting with Baseline visit
- Follow-Up Phase of 12-weeks (84±5 days). This will comprise of Closure Confirmation period of 4 weeks (28±3 days) and Observation period of 8 weeks (56±5 days).

Subject Number Assignment: The Subjects will be assigned randomization number using an interactive web-based randomization system (IWRs). Prior to randomization, Subjects will be stratified by location (plantar or non-plantar) and size ($<5\text{ cm}^2$ or $\geq 5\text{ cm}^2$) of the Target Ulcer solely for the purpose of bringing homogeneity among the three treatment Groups in proportionately. Once a randomization number has been assigned, it cannot be re-assigned to any other Subject.

Application of Treatment: Subjects in the Study will receive treatment twice daily during the 12-weeks of Treatment Phase or up to the Target Ulcer Closure, whichever is earlier. During this period, the twice daily treatment to the Subjects in all the arms of the Study will be administered

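### The primary comparison, Galnobax plus SoC versus SoC alone, is assessor-blinded with subject shielding rather than double-blind, and two avoidable cues to the arm remain

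*Combined protocol and SAP*

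**What the plan says.** Section 4.1 gives the label: "This Study is a Phase 3, multicenter, randomized, double-blind, parallel-group Study". Section 6.3 repeats it and lists the blinded parties: "This is a double-blind study wherein the Investigator, the Sponsor, the Subject, the CRO and the Study Nurse Coordinator will be kept blinded".

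The same section names the staff who are not blinded. On the nurse: "The Study Nurse who will administer treatment to the Subject (twice daily during Treatment Phase) will be unblinded". On the site: "There will be one unblinded Investigator per site who will administer the treatment during each treatment visit of the Subject". It also mentions an unblinded CRC. One limit is placed on what the first two know: "the unblinded Investigator and Study Nurse will still remain blinded to whether the Study drug applied is Galnobax® or Vehicle gel".

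The subject is to be blinded by a shield: "The blinding of the Subject will be ensured by the Study Nurse by using shield while treating the Target Ulcer". This sentence is not restricted to any arm.

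A separate procedure covers transport of the gel and the compliance check. Its trigger begins "In case the Subject is staying far from the site (i.e. 40 km or more from the site) and/or Nurse is unable to visit", the second condition being that the nurse cannot come to the site every week. In those cases the nurse places "used IP tubes and Study diary in this box which will be locked and sent to the site with the Subject". The nurse and the unblinded CRC hold the keys.

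Section 6.3 leaves the closure decision and its confirmation to the blinded Investigator. Section 9.4.2 limits the primary efficacy analysis to Group 1 (Galnobax plus SoC) and Group 2 (SoC only).

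**The concern.** The label describes a pair of arms that the efficacy analysis does not compare. Galnobax versus Vehicle can be double-blind. Galnobax plus SoC versus SoC alone cannot, because one arm receives gel and the other does not, and the people giving twice-daily care can see which.

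Two routes to bias follow. First, care could differ between arms: the nurse who knows gel versus no gel also dresses the ulcer and records off-loading and missed applications (6.4). Blinded assessment does not protect against that. Second, the blinded Investigator could learn the arm, either from a subject arriving with a box that the protocol describes only for gel, or from residue on the ulcer. Closure is a judged endpoint, so a cue to the assessor could act on it directly. It could also shift the date of first observed closure, which defines the time-to-closure endpoint.

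**Working it through.** **Who knows what, by comparison.** Section 6.1.2 gives the SoC arm the same morning and evening steps as the gel arms, minus the gel.

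| Comparison | Study Nurse, unblinded Investigator, unblinded CRC | Assessor | Subject |
|---|---|---|---|
| Galnobax + SoC vs SoC (primary) | Know gel vs no gel | Blinded, subject to the cues below | Shielded |
| Galnobax vs Vehicle | 6.3 keeps nurse and Investigator blind; labels and kits are common to both gels (6.2.2) | Blinded | Blinded |

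An SoC subject is therefore identified with certainty. At 3:3:1 allocation a gel subject is on Galnobax with probability 3/(3+1) = 0.75. Unblinded contact amounts to at most 2 per day × 84 days = 168 applications per subject, fewer when the ulcer closes early. That counts exposure; it does not measure bias.

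**Cue 1, the box.** It holds gel tubes and the Study diary. The diary exists in all arms; tubes exist only in the gel arms. Section 6.3 does not say whether an SoC subject who meets the distance or nurse-visit condition carries a box, nor that it is handed over out of the blinded Investigator's sight.

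**Cue 2, the order of steps.** Section 6.1.2 addresses its application steps to the unblinded Investigator and nurse. In every arm the morning steps begin with dressing removal and a saline rinse of the ulcer; in the evening the ulcer itself is not rinsed. The gel length is calculated from the area measured at that visit, so measurement comes before new gel. But sections 8 and 8.1 do not say that the old dressing comes off and the rinse is done before the blinded Investigator looks. Gel from the previous evening could then still be present. Section 2.3.2 describes the gel as adhering to tissue; 6.2.2 calls it colorless, which weakens the cue.

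**The planning figures (9.2).** p₁ = 0.39 (SoC), p₂ = 0.60 (Galnobax), difference 0.21, two-sided α = 0.05, power 90%. With pooled variance and p̄ = 0.495,

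n = [1.96·√(2 × 0.495 × 0.505) + 1.282·√(0.39 × 0.61 + 0.60 × 0.40)]² / 0.21² → 118 per group,

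against 120 stated (power 90.7% at 120). The plan's figure reproduces, and the blinding point does not depend on it.

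**Size of assessment bias, illustration.** Only two errors favour Galnobax:

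- Galnobax non-closers judged closed: 5% × (1 − 0.60) = 5% × 40% = 2.0 points.
- SoC closers judged open: 5% × 39% = 1.95 points.

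Each is a little under a tenth of the planned difference (2.0/21 = 9.5%; 1.95/21 = 9.3%). The 5% is assumed; the documents give no misjudgement rate.

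**Size of unequal care, illustration.** Assume no drug effect, 39% closure in SoC, 120 per arm, and a care-driven gain b in the gel arm. The chance of a significant result favouring gel is Φ[(b − 1.96·SE₀)/SE₁], with SE₀ pooled and SE₁ unpooled. For b = 0.05: SE₀ = √(0.415 × 0.585 × 2/120) = 0.0636 and SE₁ = √((0.39 × 0.61 + 0.44 × 0.56)/120) = 0.0635, giving 12.0%. For b = 0.03 and 0.10 the results are 6.8% and 34.4%. The nominal one-direction rate is 2.5%. The documents give no basis for any value of b.

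**The case against.** The strongest reply is that the protocol hides nothing and protects the endpoint where it matters. Section 6.3 names the unblinded staff alongside the double-blind label and never claims that the nurse is blind. Closure requires full re-epithelialization without drainage, is decided by the blinded Investigator, and must hold at two further visits, 14 and 28 days after end of treatment. Gel has stopped by then, so residue cannot cue the confirming assessments, and a false closure would have to survive three observations. The ulcer is also photographed at each follow-up visit.

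Most of this stands. The label by itself is largely a matter of terminology, and residue can act mainly at the first observation. The confirmation visits protect against false closures, however, not against closures withheld; those are corrected only by the later weekly visits, if any remain before week 12. None of these safeguards touches unequal care.

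A reader might infer more than the text supports:

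- That the shield is used only in the gel arms. The sentence has no such limit.
- That the box is a blinding device, or that SoC subjects are known not to carry one. It is a conditional transport and compliance procedure, and the text is silent on SoC.
- That nobody is assigned to remove the dressing and rinse. Section 6.1.2 assigns both to unblinded staff; only the order relative to the assessment is missing.
- That misjudging 5% of SoC non-closers (61%) or Galnobax closers (60%) would inflate the effect by about 3 points. Those errors can only turn an SoC failure into a success or a Galnobax success into a failure, so both shrink the difference.

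**Conclusion.** The primary comparison is assessor-blinded with subject shielding; only Galnobax versus Vehicle is double-blind. The documents do not show that the assessor's blinding fails. They show two places where it could leak without need: the box procedure and the unstated order of steps before the assessment.

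At the planning rates the assessment bias favouring Galnobax is about 2.0 points (Galnobax non-closers) or 1.95 points (SoC closers) for each 5% misjudged, against 21 planned. Both figures rest on an assumed 5% and precede any allowance for the confirmation and later weekly visits, so the net effect on the primary endpoint should be smaller. Unequal care is a residual risk of the chosen comparator; its size cannot be estimated from the documents. This is a low-severity point, worth acting on because the remedy is cheap.

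**What to change.** 1. In 4.1 and 6.3, state who is blind for each comparison: assessor-blinded with subject shielding for Galnobax plus SoC versus SoC, double-blind for Galnobax versus Vehicle.
2. In 6.3, require the same closed, locked box for subjects in all three arms who meet the distance or nurse-visit condition, handed to the unblinded CRC out of the blinded Investigator's sight.
3. In 6.1.2 and section 8, state that at site visits unblinded staff complete the dressing removal and morning saline rinse already specified, in every arm, before the blinded Investigator assesses the ulcer. This must be reconciled with the separate morning and evening instructions in 6.1.2 and should add no wound-care step.

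The comparator, endpoint, sample size and staffing stay as they are. The cost is a less favourable label, some extra boxes and a few minutes per visit. These changes close the two cues; they do not remove the risk of unequal care, which the clearer description at least makes visible.

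### Section 6.3 has some subjects carry IP tubes to every treatment visit in a locked box, with no matching box for SoC-only subjects, so the box can reveal gel versus SoC

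*Combined protocol and SAP*

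**What the plan says.** Section 6.3 names those who must not know the allocation: "the Investigator, the Sponsor, the Subject, the CRO and the Study Nurse Coordinator will be kept blinded to the randomization throughout the Study". This covers both the subject and the Investigator who judges closure. The one measure given for the subject's blind acts at the dressing change: "The blinding of the Subject will be ensured by the Study Nurse by using shield while treating the Target Ulcer".

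The section then adds a procedure for transporting IP and checking compliance. It applies when the subject lives 40 km or more from the site "and/or Nurse is unable to visit every week to the site for treatment compliance check". Its steps are:

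- Start: "IP will be issued to the study Nurse at the time of the randomization visit along with study diary in an aluminum box".
- Keys: "One key of this lock will be with the study Nurse and other with the unblinded CRC at the site".
- Weekly trip to the site: "study Nurse will keep used IP tubes and Study diary in this box which will be locked and sent to the site with the Subject".
- At the site: "Site unblinded CRC will take aluminum box from the subject and will check IP compliance as well as study diary".
- Return trip: "These materials will be kept in the aluminum box which will be locked and given to the Subject for handing over it to the study", with the nurse as recipient.

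The cycle repeats at all treatment visits. Four other places bear on it:

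- Section 6.2.1 defines IP as Galnobax and Vehicle gel.
- Section 6.1.2 gives the SoC regimen without any gel step.
- Section 6.3 sends IP to the nurse but SoC material to the subject.
- Section 6.4 issues the study diary without restriction by group and requires the nurse to keep its entries from the subject.

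**The concern.** The shield hides the treatment only while it is being applied. The box is a separate cue: the subject handles it on every trip and may bring it to the visit at which the blinded Investigator examines the ulcer. Each step is written around IP tubes, which Group 2 does not have, so whether there is a box, and what it holds, can depend on the arm.

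Group 1 (Galnobax plus SoC) versus Group 2 (SoC only) is the sole efficacy comparison (section 9.4.2), so gel versus SoC is the part of the blind that matters most. A subject who works out the arm may off-load differently, score pain differently on the 0 to 10 scale of Attachment 4, or report adverse events differently. An assessor who works it out decides the primary endpoint. Section 6.3 itself relies on blinded assessment of closure to control bias.

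**Working it through.** **1. The plan's own figure.** Section 9.2 asks for 120 evaluable subjects per group for 39% versus 60% closure, two-sided alpha 0.05 and 90% power. With pooled variance, n = [1.960·√(2·0.495·0.505) + 1.282·√(0.39·0.61 + 0.60·0.40)]² / 0.21² = 118 per group, and 120 per group gives 90.7% power. Allowing for 20% drop-out, 240/0.8 = 300. The figure reproduces and is not in dispute here; it supplies the group size for step 4.

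**2. What each group would put in a box under 6.3.**

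| Group | Tubes | Diary | Box described? |
|---|---|---|---|
| 1 Galnobax + SoC | yes | yes | yes |
| 3 Vehicle + SoC | yes | yes | yes |
| 2 SoC only | none | yes | not stated |

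Groups 1 and 3 look alike, so the box cannot separate Galnobax from Vehicle. For Group 2 there are three possibilities:

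- *No box.* Any box in sight then marks gel. Under 3:3:1 allocation the chance of gel before seeing it is (3 + 1)/7 = 57%; after seeing it, 100%. Between Groups 1 and 2 alone, the chance of Group 1 goes from 50% to 100%.
- *A box holding only the diary.* Presence then tells nothing, and 57% stays 57%. Weight and sound remain as cues: under section 6.2.2 a kit is four 15 g aluminium tubes with two boxes of measuring strips. The number of tubes in the box on a given trip is not stated.
- *An indistinguishable box.* No cue.

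Followed as written, the procedure leads to one of the first two. Nothing in it provides for the third.

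**3. The route to the assessor.** The unblinded CRC receives the box at the site, and the blinded Investigator assesses the ulcer at the same weekly visit. The documents do not say which comes first, nor that the box is kept out of the Investigator's sight. Exposure is possible but not stated.

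**4. Size.** If a share *f* of subjects use the box and knowledge of the arm moves the difference in judged closure among them by *b*, the overall difference shifts by *f·b*. The documents give neither quantity. For scale only, assume no true effect, 39% closure and 120 per group. The two-sided rejection rate is Φ(d/SE − 1.96) + Φ(−d/SE − 1.96), where d = f·b, p = 0.39 + d and SE = √[0.39·0.61/120 + p(1 − p)/120].

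| f (assumed) | b (assumed) | d | rejection rate |
|---|---|---|---|
| 10% | 5 points | 0.5 points | 5.1% |
| 10% | 10 points | 1.0 point | 5.3% |
| 25% | 10 points | 2.5 points | 6.8% |

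For the last row, SE = √[(0.2379 + 0.2428)/120] = 0.0633 and d/SE = 0.395, giving Φ(−1.565) + Φ(−2.355) = 0.068. These rows show how the effect scales; they are not estimates. They also assume that every box user's allocation is discovered.

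**The case against.** The strongest reply is that the protocol is silent, not wrong. It never says that SoC-only subjects go without a box. Their diary has to reach the site too, and its entries must be hidden from them, so a closed container would be natural. A reader might infer from 6.3 that the box shows the arm; the documents do not support that, because if SoC subjects carry a diary box its presence alone proves nothing. A subject also sees only their own box. The box is locked, the subject holds no key, and the person receiving it is the unblinded CRC. Handover order could be covered when blinded and unblinded roles are discussed at site initiation (section 10.1.5.1).

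The endpoint also resists influence. Closure needs complete re-epithelialization without drainage, confirmed at two later visits. Those visits, FU1 and FU2, fall outside the box procedure. Ulcer area is measured by camera (section 8.1), and closed ulcers are photographed during follow-up (section 8).

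All of this stands as a limit on the size of the problem. It does not remove it. A lock hides the contents but not the existence, weight or sound of a box, and a diary-only box is still different from one with tubes. Whatever the subject or assessor has inferred by the end of treatment is not undone at FU1 and FU2. With about 40 sites, leaving the point unwritten means that each site decides it alone.

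**Conclusion.** The concern holds in this form: a written logistics rule can put an arm-dependent object in the hands of a blinded subject, with no provision for matching it in Group 2 and no order of handover relative to the blinded assessment. It can reveal gel versus SoC to the subject, and possibly to the assessor. The trigger is wider than distance, since nurse availability alone is enough.

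The size cannot be derived from the documents. It depends on the unstated share of subjects using the box, on what Group 2 subjects actually carry, and on how far knowledge of the arm could move a closure judgement. Two stronger inferences should be resisted:

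- *A large inflation of type I error.* This needs a big assumed share and a big assumed swing. A swing of 20 points, for example, would nearly equal the whole planned difference of 21 points, and nothing in the documents supports that for an endpoint defined and confirmed as this one is.
- *Forced exits.* Section 7.2, item 7 requires discontinuation when a subject's blinding is compromised, but nothing suggests that carrying a locked box would be recorded as such.

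This is a correctable weakness in the blind, worth an amendment. It does not by itself undermine the primary analysis.

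**What to change.** Amend section 6.3 in two respects:

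1. Every subject who meets the distance or nurse criterion, in all three groups, carries an identical locked box. It holds the study diary and, for SoC-only subjects, filler such as dressing packs so that it is not noticeably different to lift or handle. Exact weight matching is unnecessary, because tube weights change from week to week anyway.
2. The unblinded CRC takes the box before the subject meets the blinded Investigator and returns it only after all blinded assessments at that visit are complete.

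The cost is a few sentences, plus extra boxes and filler for SoC-only subjects who meet the trigger. No added staff are needed, because the unblinded CRC already handles the box.
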